1.6. List of Changes

Amendment 7, leading to version 8.0 of the protocol, date June 21, 2022

All changes are clearly identified in the track-changes version of the amendment.

Major changes		
Description of changes	Reason for change	Sections affected
Disordered proliferative endometrium has been re-included as an exclusion criterion.	The FDA doesn't agree with the modification of IC#5 and EC#4 introduced with PA 6.1. Postmenopausal women with a screening endometrial biopsy histological diagnosis of disordered proliferative endometrium must not be enrolled.	2 Study Synopsis 8.2 Inclusion and Exclusion Criteria
Disordered proliferative endometrium has been re-included as a reason for discontinuation.	The FDA doesn't agree with the modification to the stopping criteria for non-hysterectomized women introduced with PA 6.1. Women with a biopsy and histological evidence of disordered proliferative endometrium must not be exposed to continued unopposed estrogen treatment.	2 Study Synopsis 5.4 Risk-benefit Assessment 7.1.1 Trial Design (Figure 1) 8.3. Subject Discontinuation and Replacement Procedures 10.4.1. Treatment Emergent Adverse Events 10.4.8. Endometrial biopsy in non-hysterectomized subjects. 10.4.10. Endometrial safety assessment and stopping rules (non-hysterectomized subjects only)
Minor changes		
Description of changes	Reason for change	Sections affected
[REDACTED]	Update of ICON responsible party.	1.2 Contact Information 1.5. CRO Approval and Signature Page

Table continued on the next page

Minor changes		
Description of changes	Reason for change	Sections affected
DPE has been re-included as an endometrial event for which administration of P4 200 mg (once a day, for 14 consecutive days) should be considered by the Investigator.	DPE has been re-included as an endometrial event leading to discontinuation (see Major Changes).	2. Study Synopsis 5.4 Risk-benefit Assessment 10.4.1 Treatment Emergent Adverse Events 10.4.8 Endometrial biopsy in non-hysterectomized subjects 10.4.10 Endometrial safety assessment and stopping rules (non-hysterectomized subjects only)
A Clinical Event Committee is created to support the DSMB in the adjudication of the cardiovascular and thrombotic events that arise during the course of the study.	The DSMB has requested the creation of a Clinical Event Committee.	10.5 Data Safety Monitoring Board

Amendment 6.1, leading to version 7.1 of the protocol, date July 30, 2021

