8. SUBJECT SELECTION AND DISCONTINUATION/WITHDRAWAL OF SUBJECTS

8.1. Source and Number

This will be a multicenter trial performed in multiple study sites in the United States of America and Canada. Subjects will be recruited by the investigator from his/her patients or will be recruited by recruitment campaigns. Subjects must seek treatment for the relief of menopausal symptoms, or subject may already be treated for menopausal symptoms and willing to discontinue their current treatment.

All investigators must keep a record of subjects who were considered for enrollment and were consented, but were never enrolled e.g., subject screening log to address concerns over selection bias.

This trial will enroll a total of approximately 1,000 subjects; ~600 subjects ~200 per treatment arm) in the Efficacy Study part and ~400 subjects in the Safety Study part of the trial. Enrollment will stop when the minimum required number of subjects in each study group and study part is enrolled.

The number of completers after three months of treatment in the Efficacy Study part is anticipated to be around 435, anticipating a drop-out rate of 35% and 20% for non-hysterectomized and hysterectomized women, respectively. The number of completers after 12 months of treatment is anticipated to be ~300, anticipating a drop-out rate of 50% after one year of treatment.

The number of completers in Safety Study part after 12 months of treatment is expected to be ~200, anticipating a drop-out rate of 50%.

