8.2.2. Criteria for Exclusion

Subjects will not be allocated to treatment if they meet one of the following exclusion criteria:

1. History of malignancy, with the exception of basal cell or squamous cell carcinoma of the skin if diagnosed more than 1 year prior to the Screening visit¹⁵;
2. Any clinically significant findings found by the Investigator at the breast examination and/or on mammography suspicious of breast malignancy that would require additional clinical testing to rule out breast cancer (however, simple cysts confirmed by ultrasound are allowed);
3. PAP test with atypical squamous cells undetermined significance (ASC-US) or higher (low-grade squamous intraepithelial lesion [LSIL], atypical squamous cells cannot exclude high-grade squamous intraepithelial lesion [HSIL] [ASC-H], HSIL dysplastic or malignant cells) in sub-totally hysterectomized and non-hysterectomized subjects¹⁶. Note: ASC-US is allowed if a reflex human papilloma virus (HPV) testing is performed and is negative for high risk oncogene HPV subtypes 16 and 18;
4. For non-hysterectomized subjects:
 - a. History or presence of uterine cancer, endometrial hyperplasia, or disordered proliferative endometrium;
 - b. Presence of endometrial polyp;
 - c. Undiagnosed vaginal bleeding or undiagnosed abnormal uterine bleeding;
 - d. Endometrial ablation;

¹⁴ A report or a statement on letterhead from the subject's physician documenting both ovaries were removed is needed.

¹⁵ The exception is only for basal cell carcinoma or squamous cell carcinoma of the skin if either of them were diagnosed more than one year prior to the screening of the subject.

¹⁶ As indicated by written documentation of a prior test performed within 18 months prior screening or by a test performed at screening.

- e. Any uterine/endometrial abnormality that in the judgment of the investigator contraindicates the use of estrogen and/or progestin therapy. This includes presence or history of adenomyosis or significant myoma;
- 5. Systolic blood pressure (BP) higher than 130 mmHg, diastolic BP higher than 80 mmHg¹⁷ during screening;
- 6. History of venous or arterial thromboembolic disease (e.g., superficial or deep vein thrombosis, pulmonary embolism, stroke, myocardial infarction, angina pectoris, etc.), or first-degree family history of VTE;
- 7. History of known acquired of congenital coagulopathy or abnormal coagulation factors, including known thrombophilia's;

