10.5. Data Safety Monitoring Board

An independent DSMB will be established to perform ongoing safety surveillance. The voting members on the DSMB are external to the Sponsor and are not involved with the trial in any other way and have no competing interests that could affect their roles with respect to the trial.

During the conduct of the study, the safety data of the study will be collected on an ongoing basis and provided to the DSMB. The DSMB will monitor the general safety and the endometrial safety of the trial at an appropriate frequency as provided in the DSMB charter and will make recommendations to the Sponsor regarding steps to ensure the safety of the trial subjects. The DSMB will be supported by a Clinical Event Committee who will adjudicate cardiovascular and thrombotic events in a consistent and unbiased manner throughout the course of the study.

More details on the DSMB, including the composition, responsibilities, timing and organization of the meetings and administrative structure will be described in a separate DSMB charter.

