#### **7.7.1.1 Adverse Events**

All AE verbatim descriptions will be coded using the MedDRA, version 24.1 or the most updated version.

---

All AEs will be listed, TEAEs will be summarized as definition of TEAE are described in [Section 6.1](#). Details for imputing missing or partial start dates of AEs are described in Section 6.2.2.

In summaries by SOC and PT, TEAEs will be sorted by decreasing frequency within each SOC and PT. In summaries by PT, TEAEs will be sorted by decreasing frequency.

If a subject experiences the same TEAE more than once with different intensities, then the event with the highest intensity will be tabulated in 'by intensity' tables. TEAEs with a missing intensity will be presented in the summary table as an intensity category of 'Missing'.

If a subject experiences multiple TEAEs within the same PT (SOC), then the subject will be counted only once for that PT (SOC).

Relationship to study drug, as indicated by the Investigator, is classified as 'Highly probable', 'Probable', 'Possible', 'Unlikely' and 'Not Related'. If a subject experiences multiple TEAE within the same PT(SOC), the TEAE with the strongest relationship to study drug will be counted for that PT(SOC). Relationship will be summarized as 'Related' and 'Not Related'. Adverse Events with investigator indicated drug-event relationship of 'Unlikely' and 'Not Related' will be classified as 'Not Related' to study drug, while Adverse Events with drug-event relationship documented as 'Highly probable', 'Probable', 'Possible' will be considered as 'Related' to study drug. Where TEAEs have a missing relationship to study drug will also be considered as 'Related' to study drug.

Adverse Events of Special Interest (AESI) are a subset of TEAEs that include the events listed below:

- Vaginal bleeding events grade 2 as assessed using the vaginal bleeding events scale
  - Events resulting from endometrial biopsy reading limited to:
    - Disordered proliferative endometrium;
    - Simple hyperplasia without atypia;
    - Complex hyperplasia without atypia;
    - Simple hyperplasia with atypia;
    - Complex hyperplasia with atypia;
    - Carcinoma

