- Serious TEAEs by SOC, PT and maximum intensity;
- Serious TEAEs of reproductive system and abdominal pain by SOC, PT and maximum intensity by hysterectomy status (hysterectomized and non- hysterectomized), as defined in [Table 4](#);
- Drug related serious TEAEs by SOC, PT and maximum intensity;
- Drug related serious TEAEs of reproductive system and abdominal pain by SOC, PT and maximum intensity by hysterectomy status (hysterectomized and non- hysterectomized), as defined in [Table 4](#);

- TEAEs leading to deaths, by SOC, PT and maximum intensity;
- TEAEs of reproductive system and abdominal pain that leading to deaths, by SOC, PT and maximum intensity by hysterectomy status (hysterectomized and non- hysterectomized), as defined in [Table 4](#);
- Drug related TEAEs leading to deaths, by SOC, PT and maximum intensity;
- Drug related TEAEs of reproductive system and abdominal pain that leading to deaths, by SOC, PT and maximum intensity by hysterectomy status (hysterectomized and non-hysterectomized), as defined in [Table 4](#);
- AESI by SOC, PT and hysterectomy status (hysterectomized and non- hysterectomized);
- AESI by SOC, PT and maximum intensity and hysterectomy status (hysterectomized and non-hysterectomized);
- Venous thromboembolism events (VTE) incidence and cardiovascular events incidence, with additional information as defined below:

Number of Subjects with at least one event in each of the following categories:

- VTE including:
  - Pulmonary embolism and Pulmonary embolus.
  - Deep venous thrombosis.
- Cardiovascular events including:
  - Myocardial infarction, Acute myocardial infarction and Myocardial ischaemia.
  - Cerebrovascular accident, Transient ischaemic attack, Ischaemic stroke and Subarachnoid haemorrhage.
  - Peripheral occlusive disease.
  - Angina unstable and Angina pectoris terms
- Other thrombotic events

Number of VTE and CV events, n per 1000 patient-years (n/1000 PY) of exposure will be presented, which is defined as the summation of number of years for all the subjects at risk, calculated as:

$$\text{Events per 1000 Patient-Years} = n / PY * 1000$$

where,

n = number of events in each group.

PY = (End of Treatment Date – First treatment date + 1)/365.25 or

(cut-off date – First treatment date + 1)/365.25 for ongoing subjects.

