**Table 4: Reproductive system and abdominal pain preferred terms**

	AEBODSYS	AEDECOD
Reproductive system	Reproductive system and breast disorders	

Abdominal pain	Gastrointestinal disorders	Abdominal pain Abdominal pain lower Abdominal pain upper
----------------	----------------------------	--

Listings will be provided for the Included Set (including flagged for TEAEs) include:

- AEs
- AEs leading to deaths
- All SAEs (including serious AESI)
- AEs leading to dose interruption and discontinuation
- All AESI (including serious and non-serious AESI)
- VTE in the cardiovascular and cerebrovascular system

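### The Safety Study part SAP counts VTE and cardiovascular events from coded terms only, and the Clinical Event Committee's adjudicated outcomes have no place in any planned table or listing

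*SAP*

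**What the plan says.** **Event source.** SAP 7.7.1.1 opens with the coding rule: "All AE verbatim descriptions will be coded using the MedDRA, version 24.1 or the most updated version". Later in the section it plans "Venous thromboembolism events (VTE) incidence and cardiovascular events incidence, with additional information as defined below". The VTE group names pulmonary embolism and deep venous thrombosis. The cardiovascular group names coronary, cerebrovascular, peripheral occlusive and angina terms. A last row, for other thrombotic events, has no terms under it. The rate is n / PY × 1000, where "n = number of events in each group" and PY runs from first treatment to end of treatment. Among the listings is one for "VTE in the cardiovascular and cerebrovascular system". The SAP mentions neither adjudication nor a committee.

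**Protocol 8.0.** Section 10.5 of the protocol states: "The DSMB will be supported by a Clinical Event Committee who will adjudicate cardiovascular and thrombotic events in a consistent and unbiased manner", throughout the study. The list of changes (section 1.6) dates this to Amendment 7 and gives the reason: "The DSMB has requested the creation of a Clinical Event Committee".

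**Versions.** The synopsis of the current protocol is version 8.0, 21 June 2022. SAP 3.0 is dated 7 July 2022. Section 1 of the SAP names Protocol 7.1 as its basis, and section 9 lists nothing later. The only change logged for SAP 3.0 concerns biopsy diagnoses. SAP section 8, on departures from the protocol, lists three dropped analysis sets and nothing from Amendment 7.

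**The concern.** General safety is the primary objective of this study part, and thromboembolic disease is one of the class risks named in Protocol 5.4. The VTE and cardiovascular rate is the only exposure-adjusted rate in this SAP. Two versions of the same events will exist: the coded term from the investigator's report and the committee's adjudicated outcome. The SAP uses the first and is silent on the second.

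Followed as written, the plan reports the coded count and leaves the adjudicated result out of every table and listing. If the adjudicated result is added later, the choice of which count to lead with is made after both are known, in an arm where everyone knows the treatment.

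The coded count also leaves one row open. With no term list for other thrombotic events, someone has to decide what goes there once the events are in view. For example, exclusion criterion 6 (Protocol 8.2.2) reads "History of venous or arterial thromboembolic disease (e.g., superficial or deep vein thrombosis, pulmonary embolism", so the protocol treats superficial vein thrombosis as thromboembolic disease. The SAP's VTE group does not name it.

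**Working it through.** **1. Texts side by side**

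| Item | Protocol 8.0 (21 June 2022) | SAP 3.0 (7 July 2022) |
|---|---|---|
| Protocol basis | 8.0 | 7.1 |
| Cardiovascular and thrombotic events | Adjudicated by a committee supporting the DSMB (10.5) | Named terms from coded adverse events (7.7.1.1) |
| Adjudicated outcome in a table | Not addressed (12.8) | None |
| Adjudicated outcome in a listing | Not addressed | None |

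The SAP does have a counting rule. What it lacks is any place for the outcomes that Amendment 7 created.

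**2. The plan's own figure**

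Protocol 8.1: "The number of completers in Safety Study part after 12 months of treatment is expected to be ~200, anticipating a drop-out rate of 50" (per cent), from about 400 women.

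Completers = 400 × (1 − 0.50) = 200, which reproduces the stated figure. The same arithmetic for the Efficacy Study part gives 300 × 0.65 + 300 × 0.80 = 435, also as stated.

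**3. Exposure**

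Patient-years = 200 completers × 1 + 200 dropouts × f, where f is the mean fraction of the year that a dropout is treated. The documents do not give f.

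- f = 0 (all leave at the start): 200
- f = 0.5 (assumed): 200 + 100 = 300
- f = 1 (all leave at the end): 400

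The SAP's divisor of 365.25, with end of treatment between day 365 and day 371, gives 299.8 to 304.7 at f = 0.5. Rounding to 300 does not matter.

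**4. Weight of one event**

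1000 / 300 = 3.3 per 1000 patient-years; 1000 / 400 = 2.5; 1000 / 200 = 5.0.

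**5. Illustration at 300 patient-years**

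The event counts are invented for scale. The exact Poisson limits are added here; the SAP specifies no interval for this rate.

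| Events | Rate per 1000 PY | Exact 95% limits |
|---|---|---|
| 0 | 0 | 0 to 12.3 |
| 1 | 3.3 | 0.1 to 18.6 |
| 2 | 6.7 | 0.8 to 24.1 |

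If adjudication turned one event into two, the rate would double. The upper limit would move from 18.6 to 24.1.

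**6. Disordered proliferative endometrium (DPE)**

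Protocol 10.4.8 and 10.4.10 now make DPE a reason to stop treatment. The Figure 1 note in SAP 3.1 and the later text under Discontinuation in SAP 7.7.1.12.1 keep the version 7.1 rule, under which such women continue. The Safety Diagnosis text and the first sentence under Discontinuation say stop. In the consensus analysis DPE falls in Category 1, benign (Appendix 5, Table 8), so the hyperplasia and carcinoma frequencies are the same under either wording.

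**The case against.** The strongest reply is that the SAP already has a rule (coded terms, named groups, a formula) and that nothing in the protocol conflicts with it. The committee was created for the DSMB, is logged as a minor change to section 10.5 alone, and appears in no endpoint or analysis section. The arm is single and open-label, with no formal test. Protocol 10.4.1 requires every VTE and arterial thromboembolism to be reported as an SAE, and the SAP lists all SAEs, so a reader can see each coded event. The DSMB charter and the table templates were not supplied. Whether committee outcomes reach the clinical database, and whether events before Amendment 7 were adjudicated, cannot be checked.

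Most of this stands, and it rules out several stronger readings.

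- A reader might infer that the SAP has no rule for counting these events. It has one; it only omits the adjudicated outcomes.
- A reader might infer that the SAP breaches the protocol. It does not, because the protocol does not say how the committee's outcomes enter the report.
- A reader might infer that superficial vein thrombosis will be lost. The VTE terms are introduced as inclusions, not as a complete list, and the row for other thrombotic events could take it. Criterion 6 is an eligibility rule, not an endpoint definition. The missing term list does not come from Amendment 7, but it still needs filling.

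The reply does not explain why outcomes adjudicated throughout the study should be absent from every table and listing. The protocol leaves their reporting open, and the SAP is the place to settle it in advance. Possible incomplete adjudication of early events is a real drawback; it calls for flagging those events and keeping the coded count in view.

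**Conclusion.** The concern holds as a gap in the SAP. The VTE and cardiovascular incidence and rate rest on coded terms only, the SAP was not updated for Protocol 8.0, and adjudicated outcomes have no planned output. It is worth correcting because it is cheap and concerns the one exposure-adjusted rate in this part.

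The size is unknown. The figure of 3.3 per 1000 patient-years (2.5 to 5.0) is the weight of any single event in this much exposure. A reader might take it as an estimate of bias, but the documents give neither event counts nor a disagreement rate, so it is not one. It rests on 400 women treated, 50% dropout and an assumed half-year average for dropouts; the range covers the two extremes of dropout timing.

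A reader might also infer from the stale DPE wording that the endometrial results are affected. They are not: no derivation depends on it, and all biopsy readings are listed in any case. It is housekeeping.

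The SAP for the Efficacy Study part was not available. The version cited in section 1 of this SAP is dated 5 April 2022, so that version cannot reflect Amendment 7 either.

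**What to change.** Before database lock:

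1. Cite Protocol 8.0 in SAP sections 1 and 9.
2. In 7.7.1.1, specify that VTE and cardiovascular incidence and the rate per 1000 patient-years are reported on committee-adjudicated events, with the coded-term count beside them. Flag any event that was not adjudicated, including events before Amendment 7.
3. Add adjudicated outcome and category to the VTE listing.
4. Give a term list for the row of other thrombotic events.
5. As housekeeping, state the DPE rule by protocol version: stop before 7.1, continue under 7.1, stop under 8.0.

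The cost is a text revision, one extra row in an existing table, two columns in an existing listing and a short term list. It assumes that the committee's outcomes can be transferred to the analysis database, which should be confirmed first. Trial conduct and the biopsy derivations stay as they are.

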## 7 STATISTICAL METHODS

### 7.1 General Statistical Conventions

All statistical procedures will be completed using SAS version 9.4 or higher, there is only one treatment group, thus no formal statistical analysis will be performed.

Confidence intervals (CIs) will be presented as 2-sided 95% CIs unless specified differently in specific analysis.

Categorical variables will be summarized using frequency counts (n) and percentages in each category, percentages will be computed for subjects with non-missing value (as the denominator). If there are missing values, missing values counts will be provided. All percentages will be rounded to one digit after decimal point. The frequency counts and percentages will be presented in the form XX (XX.X %), where the percentage is in the parentheses. If the percentage of a category is '100 %', then it will be displayed as '100 %' (no decimals will be added after 100).

Continuous variables will be summarized using the number of subjects with non-missing values (n), mean, median, standard deviation (SD), minimum (min), maximum (max) and missing values counts. Missing values counts will be displayed only if there are missing values. All mean and median values will be formatted to one more decimal place than the measured value. Standard deviations will be formatted to two more decimal places than the measured value. The min and max will be displayed to the same number of decimal places as the measured value. Unscheduled visits will not be summarized in tables.

Analyses will be performed by visit, irrespective of any time window deviations, unless otherwise specified. The early discontinuation (ED) visit will be separated from the scheduled EoT- visit based on discontinuation reason. Unscheduled visits related to efficacy data will be clustered with scheduled visits based on the visit windows in [Table 5](#) of Appendix 1. Similarly, the unscheduled visit results will be clustered with scheduled visits based on the visit windows defined in [Table 6](#) (Appendix 1) for microscopic findings and laboratory endpoints and endometrial biopsy. Similarly, the scheduled visits for ECG, Procedures, Questionnaire, Vital Signs, Imaging and Findings will be based on visit window [Table 7](#) in Appendix 1.

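### SAP 7.7.1.1 gives the VTE and cardiovascular rate no confidence interval and does not define an event as a clinical episode, so a zero carries no bound and one episode could count twice

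*SAP*

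**What the plan says.** SAP 7.7.1.1 plans an incidence table for venous thromboembolism (VTE) and cardiovascular (CV) events in the single-arm, open-label Safety Study part. It has two elements.

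- **A count of women:** "Number of Subjects with at least one event in each of the following categories". Under VTE the list has two lines, "Pulmonary embolism and Pulmonary embolus" and "Deep venous thrombosis". The cardiovascular category likewise groups several cardiac and cerebral terms.
- **A rate:** "Number of VTE and CV events, n per 1000 patient-years (n/1000 PY) of exposure will be presented". The numerator is given as "n = number of events in each group". The denominator is built from "PY = (End of Treatment Date – First treatment date + 1)/365.25 or" a data cut-off for women still on treatment, and is described as the years of the subjects at risk. It does not stop at a first event.

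On intervals, SAP 7.1 says: "Confidence intervals (CIs) will be presented as 2-sided 95% CIs unless specified differently in specific analysis". That fixes the form of an interval where one is given. Section 7.7 plans counts and percentages for categorical safety data. Where the SAP wants an interval it says so: lipids and glucose (7.6.1.5), MENQOL (7.6.1.6.2), CGI (7.6.1.7) and endometrial findings (7.7.1.12 and 7.7.1.12.2). The text on the VTE and CV rate asks for none.

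**The concern.** Two things are missing, and both bear on how a sparse count will be read.

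First, without an interval the rate does not show how little the data can exclude. Protocol 5.4 names thromboembolic disease as a known risk of menopausal hormone therapy, and general safety is the primary objective of this part. The part has no control arm, so its rate will be read largely on its own. If no events occur, the table shows 0.0 with nothing beside it.

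Second, the SAP does not say whether an event is an adverse event record, a coded term or a clinical episode. Pulmonary embolism and deep venous thrombosis are separate lines. Protocol 10.4.1 allows a new record when an event deteriorates and requires a separate form for each recurrence, so one evolving episode can leave two records. The once-per-subject rule in SAP 7.7.1.1 governs counts of subjects within one preferred term or organ class. It does not merge different terms and is not applied to n.

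**Working it through.** **Inputs**

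- Target size of the Safety Study part: about 400 women (SAP section 4).
- Completers: Protocol 8.1 says "The number of completers in Safety Study part after 12 months of treatment is expected to be ~200, anticipating a drop-out rate of 50" per cent. Check: 400 × (1 − 0.50) = 200, which reproduces the stated figure.
- Treatment period: 52 weeks, taken as 1 year.
- Patient-years (PY): **not given in the documents, so assumed.** The 200 completers contribute 1 year each. The 200 who drop out contribute an average fraction f of a year:
  - f = 0: 200 + 0 = 200 PY
  - f = 0.5: 200 + 100 = 300 PY (working value)
  - f = 1: 200 + 200 = 400 PY

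**Formulas**

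- Rate, as in the SAP: n / PY × 1000.
- Exact Poisson 95% limits: lower = χ²(0.025; 2n)/2 and upper = χ²(0.975; 2n + 2)/2, each divided by PY and multiplied by 1000.
- For n = 0 the upper limit on the count is 3.69. For n = 1 the limits are 0.025 and 5.57.

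**Results, per 1000 PY**

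| Assumed PY | Zero events: printed rate | Zero events: exact 95% upper limit | One woman, counted once (95% CI) | Same episode as two records: printed rate |
|---|---|---|---|---|
| 200 | 0.0 | 18.4 | 5.0 (0.13 to 27.9) | 10.0 |
| 300 | 0.0 | 12.3 | 3.3 (0.08 to 18.6) | 6.7 |
| 400 | 0.0 | 9.2 | 2.5 (0.06 to 13.9) | 5.0 |

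At 300 PY: 3.69/300 × 1000 = 12.3; 1/300 × 1000 = 3.3; 2/300 × 1000 = 6.7.

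**How easily a zero could arise.** Take a true rate of 3 per 1000 PY, purely as an illustration. The chance of seeing no event is exp(−3 × 300/1000) = exp(−0.9) = 41%. It is 55% at 200 PY and 30% at 400 PY.

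**Stopping time at the first event.** If one woman has an event at mid-year and her later time is removed, PY falls from 300 to 299.5. The rate moves from 1000/300 = 3.33 to 1000/299.5 = 3.34, a negligible change.

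**The case against.** The case for leaving the plan alone has several good parts.

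- **Women are counted.** The same section tabulates women with at least one event, with VTE as a parent category, so a woman with both diagnoses should appear once there. Listings of serious events and of VTE follow. With so few events, a reader could see one woman beside two events. It would be wrong to infer that the plan ignores women; only the rate does.
- **Double counting is possible, not stated.** A reader might infer that the plan does count one episode twice. The SAP does not say so, because it leaves the term undefined. Protocol 10.5 also sets up a Clinical Event Committee to adjudicate these events, which could merge records. However, the SAP is written on protocol version 7.1 and never refers to that committee. A double count would also raise the reported risk, not hide it.
- **A total-event rate is legitimate.** A reader might infer that failing to stop time at the first event makes the rate invalid. The formula is labelled as events per 1000 patient-years, and the effect of stopping is negligible.
- **The omission matches other adverse event outputs.** Most of the intervals the SAP requests are for efficacy endpoints, and the protocol itself asks for the interval on hyperplasia/carcinoma. Table templates are in a separate document, and the Efficacy Study part SAP is not available here, so either may say more. A reader given n and PY could derive the interval.
- **The trial does contain a control.** The Efficacy Study part randomizes 20 mg against placebo, so only this arm is uncontrolled. Protocol 12.9 has the two parts analysed separately.

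These points narrow the concern but do not remove it. No text in the SAP asks for an interval on this rate or names a method for one, and none defines n at the level of an episode or a woman.

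**Conclusion.** The point holds as two gaps in one output: no interval is specified for a sparse safety rate, and its numerator is undefined. At an assumed 300 PY, a printed 0.0 would be compatible with a true rate of up to 12.3 per 1000 PY (9.2 at 400 PY, 18.4 at 200 PY). One episode recorded twice would double the printed rate from 3.3 to 6.7 (2.5 to 5.0 at 400 PY, 5.0 to 10.0 at 200 PY).

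The sizes rest on the assumed exposure, on the planned 400 women and 50% drop-out, and on Poisson counts. The doubling also requires that each record be taken as one event, which the SAP neither states nor prevents. This is a worthwhile and nearly free improvement in what the arm can conclude. It is not evidence that the planned analysis would be wrong.

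**What to change.** In SAP 7.7.1.1:

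1. Define the main VTE rate and the main CV rate each as the number of women with at least one event in the category, already tabulated, divided by patient-years. Use adjudicated events where available, and say so.
2. Add an exact Poisson two-sided 95% interval, including the upper limit when there are zero events. Name the method, since a normal approximation has zero width at a zero count.
3. Keep the all-events rate as a secondary line, and state what counts as one event.

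Ending a woman's time at her first event is a harmless refinement that can be adopted or left. While the text is open, state the counting window. Treatment-emergent events run to the follow-up visit for non-hysterectomized women (SAP Table 1), while patient-years stop at the end of treatment.

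The cost is SAP wording and a few lines of programming, with no new data. The rate will look imprecise, which reflects the exposure this part can provide.
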